[figure not shown]

CLINICAL STUDY PROTOCOL

MCC-21-18632

SUCCEED: Engaging Black Men in CRC Screening

NCT05980182

9/08/2021

SUCCEED: Engaging Black Men in CRC Screening

Protocol Number

HM20023619

Principal Investigators

[name] (VCU)

[name] (VSU)

Protocol Version

8 September 2021

VCU Study Personnel

Principal Investigator	[name] Email: [contact]
Co-Investigator	
Research Assistant	
Student/RA	

Synopsis

Purpose

To determine the unmet needs, attitudes, barriers and facilitators of AA/Black men use of colorectal cancer screening and describe how community leaders such as barbers may act as Community Champions to educate and facilitate screening participation.

Objectives

Aim 1. Determine factors associated with self-reported CRC screening behaviors among (n=175) AA/Black men in Petersburg, VA.

Aim 2. Develop tailored S2S content for AA/Black men to be delivered using a combination of short video and text-based information optimized for delivery via QR codes for smartphones.

Aim 3. Test intervention on a sample of n=30 AA/Black men who are due for CRC screening. The primary aim is: completed CRC screening (any type) at 3months. Secondary aims are:

to collect process data to assess satisfaction and feasibility.

H1. Preliminary effectiveness of the intervention will be shown with >60% of men enrolled obtaining a CRC screen (any modality) by 12 weeks

H2. At Week 2 >80% of men enrolled will endorse an intention to be screened

H3. We will be able to recruit a sample of n=30 men into the intervention and maintain a retention rate (completion of baseline, 2 and 12 week surveys) >75%

Study Population

Survey Eligibility Criteria: Men aged 45-75 who reside in Petersburg and surrounding counties, and identify as AA/Black and have no personal history of cancer.

Intervention: For Aim 3 and additional criterion is that men have to be due for CRC screening upon study enrollment

Number of Participants

Survey: n=175

Intervention n=30

Study Design

Survey: Cross sectional; qualitative,

Intervention: single arm, pre-post Social behavioral intervention

Study Duration

Survey: 36 months total
 
Intervention: Aim 3: 12 months (once enrolled men are on study for three months)

Outcome Variables
 
Please see survey measures


Intervention: Aim 3:
 
Primary Outcome: CRC screening status at 3 months (>60%)
 
Secondary Outcomes:
 
• Intention to screen at 2 weeks (>80%)• Enrollment (target of n=30)• Maintain a retention rate (completion of baseline, 2 and 12 week surveys) >65% at 12 weeks• Viewing videos (# views, # repeat views)• Completion of baseline and follow up questionnaires (retention)• Responding to request to contact clinic/navigation services• Sharing any content with social network

Locations/Facilities
 
Surveys will be completed online
 
Recruitment for surveys will take place in-person, using social media, flyers in public spaces
 
Intervention: Aim 3: Recruitment will take place with flyers, word or mouth and presentations to introduce the study at partner and CAB member places of business and worship. These include community health clinics, local gyms, barbershops, stores, churches. We will use social media, newsletters and text messaging avenues of communication as utilized by our community and clinic partners. We will also use radio announcements on local health focused radio shows.

1 - Background/Literature Review

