4.2 Number of Participants

We require 8-10 men for the Community Advisory Board and we require n=175 Black or African American for survey in PART1. The intervention component will require n=30 men

Total study n=225

The survey component was powered on the interaction term "discrimination*preventive care engagement", both continuous, using a simulation study of 1000 runs of a logistic regression model, with the binary screening behavior response (1 = screened, 0 = not screened). A sample size of 175 subjects generates 80% power to detect a "small to moderate" effect size of 0.38 (corresponding odds ratio = 2.01, using R package "effect size") for the interaction term (continuous*continuous), at 5% level of significance, using a one-sided Z-test. To account for individuals who start but do not complete the survey we have added a buffer of 20% which gives a sample size of n=210 for the survey. The sample size has been chosen for the intervention to support an initial examination of intervention effectiveness using a one-arm design. This is a typical size that will generate pilot data on the feasibility of our approach.

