5.1 Study Design

Cross sectional survey and focus groups

Aim 3: single arm, pre-post intervention

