6.1 Sample Size

The survey component was powered on the interaction term "discrimination*preventive care engagement", both continuous, using a simulation study of 1000 runs of a logistic regression model, with the binary screening behavior response (1 = screened, 0 = not screened). A sample size of 175 subjects generates 80% power to detect a "small to moderate" effect size of 0.38 (corresponding odds ratio = 2.01, using R package "effect size") for the interaction term (continuous*continuous), at 5% level of significance, using a one-sided Z-test. To account for individuals who start but do not complete the survey we have added a buffer of 20% which gives a sample size of n=210 for the survey.

We will also conduct focus groups with n=16 men.

Total project sample size n=226

Intervention Sample Size: To perform an initial test of efficacy, satisfaction and feasibility, we will test the intervention on 30 men.

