6.2 Intervention Planned Analyses

Analysis. All variables will be described using standard methods for continuous and discrete variables and examined for completeness. An interaction effect of discrimination and engagement in preventive care will be assessed, controlling for other confounders, using a logistic regression model with the binary

response (cancer screening). Additional analysis will be conducted, controlling for demographics, via a random intercept logistic regression model. Parameter significance will be determined at the 5% level.

Research measures collected at baseline, exit and 12 weeks post are: CRC knowledge, risk perception, medical mistrust, preventive health behaviors. At 12 week only, CRC screening or intent to screen, and participant satisfaction with the intervention will be asked. Process evaluation will assess any change in CRC knowledge, risk perception, medical mistrust, and preventive health behaviors at 12 weeks.

Feasibility will be assessed using a priori benchmarks for recruitment and retention. The recruitment benchmark will be consenting 100% of the recruitment goal. Acceptance rates and reasons for declining participation will be tracked. Information on refusals will be used to modify recruitment methods as needed. Retention benchmarks will be supported if $\geq 65\%$ complete both weeks 2 and 12 follow up. Engagement benchmarks will be supported if $\geq 65\%$ of intervention completers who do not have a primary care provider chose to receive navigation services; 80% of those consented view intervention materials (e.g., click on text/graphical data, view videos, complete risk assessment).

Preliminary Efficacy. A signal for efficacy will be considered positive if among those who complete the intervention a) most ($\geq 60\%$) complete CRC screening and b) $> 80\%$ acknowledge their intent to get screened.

Follow-up interviews. Interviews will be conducted with all participants to collect in-depth, descriptive feedback on satisfaction with the intervention content, delivery modalities, ease of use and usefulness. We will also interview clinic staff and Community Champions to gain insight into facilitators and barriers to recruitment efforts and response of the community to the intervention. Suggestions for additions and alterations will be solicited from all interviews.

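### Passing 60% among 30 men does not show uptake above 60%: the primary screening proportion has no planned interval, and its pass rule differs between sections

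*Combined protocol and SAP*

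**What the plan says.** The rule for the primary outcome of Aim 3 appears in several places, in different forms.

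- Synopsis, Objectives: "H1. Preliminary effectiveness of the intervention will be shown with >60% of men enrolled obtaining a CRC screen (any modality) by 12 weeks". The denominator is men enrolled and the inequality is strict. The Synopsis list of outcomes repeats the strict 60% threshold for screening status at 3 months.
- Section 6.2, Preliminary Efficacy: "A signal for efficacy will be considered positive if among those who complete the intervention" at least 60% are screened and more than 80% state an intent to be screened. The denominator is now completers, the inequality is no longer strict, and a second condition is joined by 'and'.
- Section 5.8, outcome measures for the intervention: screening status above 60% and intention above 80% are listed with 'OR' between them.
- Section 6.1: "To perform an initial test of efficacy, satisfaction and feasibility, we will test the intervention on 30 men". Section 4.2 gives the basis for the number: "This is a typical size that will generate pilot data on the feasibility of our approach".
- Section 5.1 gives the design: "Aim 3: single arm, pre-post intervention".

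No confidence interval, reference rate, error rate or precision statement is given for the screening proportion. The 5% level in section 6.2 is attached to regression parameters.

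**The concern.** The rule compares an observed proportion with 60% and draws a conclusion from which side it falls on. H1 says effectiveness, in a preliminary sense, will be shown. Section 6.2 calls the signal positive. With 30 men the observed proportion carries an uncertainty of nearly 20 percentage points either way, and nothing in the plan requires that to be reported beside the conclusion. A reader of the results could take a pass as evidence that more than 60% of such men would be screened, when the data also fit uptake below half.

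The rule is also not the same rule throughout. The chance of passing depends on whether the denominator is enrolled men or completers, on the inequality, and on whether intent is a further requirement or an alternative. Until these are settled, the results could satisfy one section and fail another.

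**Working it through.** **Inputs.** n = 30, single arm (sections 6.1 and 5.1). Threshold 60%, strict in the Synopsis and non-strict in section 6.2. Retention benchmarks: at least 65% in section 6.2 and above 75% in H3. The documents give no reference or expected screening rate, so the true rates of 40% to 70% below are assumptions. Treating men who meet the retention benchmark as those who complete the intervention is also an assumption, since section 6.2 does not define completion.

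The plan gives no calculation behind n = 30, so there is no figure of its own to reproduce.

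**Step 1: smallest passing counts.** 0.60 × 30 = 18.
- More than 60% of 30: at least 19.
- At least 60% of 30: at least 18.
- 65% retention: 0.65 × 30 = 19.5, so 20 completers; 0.60 × 20 = 12, so at least 12.
- Above 75% retention: 0.75 × 30 = 22.5, so 23 completers; 0.60 × 23 = 13.8, so at least 14.

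**Step 2: exact 95% intervals (Clopper-Pearson).** The lower limit is the 0.025 quantile of Beta(x, n − x + 1) and the upper limit is the 0.975 quantile of Beta(x + 1, n − x).

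| Result | Observed | Exact 95% CI | Wilson 95% CI (check) |
|---|---|---|---|
| 19/30 | 63.3% | 43.9% to 80.1% | 45.5% to 78.1% |
| 18/30 | 60.0% | 40.6% to 77.3% | 42.3% to 75.4% |

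For scale only, and not as a proposed rule: the exact lower limit first exceeds 50% at 21/30 (50.6%) and first exceeds 60% at 24/30 (61.4%).

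**Step 3: chance that the screening part alone passes.** This is P(X ≥ r) for X ~ Binomial(n, p).

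| Assumed true uptake p | ≥19 of 30 | ≥18 of 30 | ≥12 of 20 completers | ≥14 of 23 completers |
|---|---|---|---|---|
| 40% | 0.8% | 2.1% | 5.7% | 3.5% |
| 50% | 10.0% | 18.1% | 25.2% | 20.2% |
| 60% | 43.1% | 57.8% | 59.6% | 55.6% |
| 70% | 84.1% | 91.6% | 88.7% | 88.0% |

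In the completer columns, p is the uptake among completers. Because counts are whole numbers, the figures do not move smoothly with the denominator: at a true 50% they are 19.2% with 21 completers and 14.3% with 22.

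**Step 4: the intent condition.** If intent above 80% is also required (section 6.2), the joint chance of passing cannot exceed these figures for the same denominator. If either condition suffices (the 'OR' in section 5.8), it cannot be lower. The documents give nothing from which to compute the joint chance.

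**The case against.** The best defence is that this is openly a pilot. H1 says 'preliminary', section 6.1 says 'initial', section 6.2 speaks of a signal, and section 4.2 describes the sample as a usual pilot size. The plan also has recruitment, retention and engagement benchmarks and interviews, so it does not rest on one figure. As a pilot screen the rule behaves tolerably: in the strict form it passes 0.8% of the time at a true 40% and 84.1% at a true 70%. All of this stands, and it is why neither the sample size nor the 60% benchmark needs to change. But the qualifying words do not supply the missing interval, and the promise in section 6.2 to describe variables by standard methods does not clearly supply one either.

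A reader might infer more than this, in three ways that the documents do not support.

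- That the rule is a coin toss. At a true 60% it does pass 43.1% or 57.8% of the time, but any cut-off on an observed proportion is missed about half the time when the truth sits on it. That is no special defect here, and adding an interval does not remove it.
- That a funding or scale-up decision turns on a single man. No such decision is tied to 60%; section 2.2 mentions scalability only as possible impact.
- That 60% is a null rate to be rejected. The plan uses it as a benchmark for the observed proportion.

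**Conclusion.** The point holds as one about what a pass can be said to show. The stated rule lets the primary conclusion follow from a bare proportion. The smallest passing results have exact 95% intervals reaching down to 43.9% (19/30) or 40.6% (18/30), so a pass does not show uptake above 60% and does not exclude uptake below half.

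The intervals rest only on n = 30 and the two inequalities; the 18/30 case also needs all 30 men to complete. The pass probabilities rest on assumed true rates and cover screening alone. At an assumed true 50% they are 10% and 18% with 30 men analysed, 25% with 20 completers and 20% with 23. The different denominators, inequalities and and/or wording are plain on the page and need no assumption.

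The finding does not show that the pilot is too small, that 60% is a poor benchmark, or that the intervention will be wrongly adopted.

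**What to change.** In section 6.2, make the primary result the number screened by 12 weeks out of all men enrolled, with its exact 95% confidence interval. Keep 60% as a descriptive benchmark on the observed proportion.

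In H1, replace 'will be shown' by 'will be estimated'. Possible wording: *The proportion of all enrolled men who are screened by 12 weeks will be estimated with an exact (Clopper-Pearson) 95% confidence interval. An observed proportion above 60% meets the pilot benchmark; meeting it does not establish that uptake exceeds 60%.*

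Then align the sections:

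- Use one inequality and one denominator in the Synopsis and section 6.2. A result among completers can be kept as a secondary description, with completion defined.
- Reconcile the 'and' in section 6.2 with the 'OR' in section 5.8 for the intent condition.
- State the benchmark as a proportion and not as a fixed count, in case enrolment is not 30.
- With all enrolled men as the denominator, say how a man with no 12-week answer is counted.

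The cost is plan wording and one routine calculation, with no extra men, visits or data. The downside is a more modest claim.

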4.3 Selection Criteria

Survey Eligibility Criteria: Men aged 45-75 who reside in Petersburg and identify as AA/Black and have no personal history of cancer.

CAB/Focus Group Criteria: adult men, identify as Black or African American, work or live in a Petersburg VA or surrounding counties and are interested in participating. They do not need to meet requirements for population based CRC screening.

Intervention Aim 3: adult men, identify as Black or African American, work or live in a Petersburg VA, aged 45-74, eligible for CRC screen at study enrollment

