One week after enrollment, men who have not engaged with the materials, completed the baseline questionnaire, or the navigation request will receive a text message aligned with the CRC risk perception and/or values elicitation that they shared with us at baseline. See table below.

Question: Which best describes your thoughts about colorectal cancer?

PARTICIPANT RESPONSE	AUTOMATED, TAILORED ANSWER
Never heard of it	Video # may interest you because it talk about CRC is and why screening can save your life!
Heard of it but not interested in screening	You might be interested to hear about the experiences of a CRC survivor. Video xx is “name” telling his story.
Heard of it and thinking about getting screened	You may want to check out video #, because it goes over the different types of screening options. The best one is the one that gets done!
Decided not to get screened	You might be interested to hear about the experiences of a CRC survivor. Video # is “name” telling his story. Video # also describes the many different screening options.
Decided to get screened	Inside the app there is a way to ask for a local clinic or screening navigator to call you directly. Check it out!
Have been screened in the past, but not recently	The best CRC screening test is the one that gets done! You may be interested in talking to a screening navigator. Inside there is a way to request a phone call from a local clinic.

Follow up: A three months after enrollment men will receive the final survey in their app and a text message notifying them that it is ready to be completed. Anyone who does not complete this survey within two weeks will be contacted by telephone by a study team member and given the option to complete it over the phone, have it emailed to them or to complete it in the app.

Table 2. Measures for intervention

Timing	CRC risk perception	Demographics	Health literacy (1 item)	Reg source of primary care	Health status	Intention to screen	Screen status	CRC knowledge	Medical mistrust
Baseline	X	x	x	x	x	x	x	x	x
2 weeks	X				x		x	x	
12 weeks	X				x	x	x		

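### Aim 3's success thresholds make no use of baseline intention, so a high share of men who had already decided to be screened could meet them without any intervention effect

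*Combined protocol and SAP*

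**What the plan says.** **Entry.** The Synopsis requires men to be due for screening at enrolment. Section 4.3 says "aged 45-74, eligible for CRC screen at study enrollment". Neither place excludes or stratifies men by intention or by an earlier decision.

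**Expected baseline states.** The tailored-message table in section 5.4 is keyed to what men reported at baseline. One of its six answers is "Decided to get screened", with its own message.

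**Success rules.** H1 in the Synopsis reads "Preliminary effectiveness of the intervention will be shown with >60% of men enrolled obtaining a CRC screen (any modality) by 12 weeks". The intention rule reads "H2. At Week 2 >80% of men enrolled will endorse an intention to be screened". Section 6.2 begins its rule with "A signal for efficacy will be considered positive if among those who complete the intervention" and then asks for at least 60% screened and more than 80% intending.

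**Design and analysis.** Section 5.1 calls Aim 3 single arm and pre-post. Table 2 marks intention and screening status at baseline. The planned change analysis is "Process evaluation will assess any change in CRC knowledge, risk perception, medical mistrust, and preventive health behaviors at 12 weeks"; intention is not in that list.

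**Sample size.** Section 6.1 says only that "we will test the intervention on 30 men". Section 4.2 adds "The sample size has been chosen for the intervention to support an initial examination of intervention effectiveness using a one-arm design". No error rate, reference rate or rationale for 60% or 80% is given.

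**The concern.** A pre-post study without a control arm has little to set its follow-up result against except each man's state at entry. Here that state is measured but does not enter the success rules. A man who intended to be screened on the day he enrolled, and still says so later, counts towards H2 exactly as a man who changed his mind. A man who had decided beforehand and would have been screened anyway counts towards H1.

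Recruitment makes some enrichment plausible: men respond to flyers, social media, radio and clinic messages about the study, then download an app and screen themselves in.

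What is at stake is the reading of a positive result. The plan says preliminary effectiveness will be shown, or an efficacy signal declared, once the percentages are passed, and section 2.2 looks ahead to scaling an efficacious version across an outreach network. As written, a pass does not distinguish an app that moved men from a sample that arrived already moved.

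**Working it through.** **Plan's own figure.** There is none to reproduce. The power calculation in sections 4.2 and 6.1 concerns the survey, and n = 30 carries no operating characteristics.

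**Thresholds as counts.** 0.60 × 30 = 18, so more than 60% means at least 19 of 30. 0.80 × 30 = 24, so more than 80% means at least 25 of 30.

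**What H2 requires for a given starting point.** If k men intend at entry and all persist, the conversions needed are 25 − k.
- k = 24: 1 of the other 6.
- k = 18: 7 of the other 12.
- k = 15: 10 of the other 15.
- k = 12: 13 of the other 18.

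A paired comparison would separate these cases. With d men moving towards intention and none moving back, the exact two-sided McNemar p-value is min(1, 2 × 0.5^d). This gives 1.0 for d = 1, 0.016 for d = 7 and 0.0002 for d = 13. H2 scores all of them as the same success.

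**Chance of meeting each threshold with no intervention effect.** Let k of 30 men have decided at entry. The count of successes is Binomial(k, p) + Binomial(30 − k, q), with p for decided men and q for the others. The exact tail comes from convolving the two. The documents give none of k, p or q; all are assumptions.

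H1 (at least 19), with p = 0.80 to 0.90 and q = 0.10 to 0.20:

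| Decided at entry | Expected number screened | P(H1 met) |
|---|---|---|
| 24 of 30 | 24×0.8 + 6×0.1 = 19.8 to 24×0.9 + 6×0.2 = 22.8 | 0.74 to 0.99 |
| 18 of 30 | 18×0.8 + 12×0.1 = 15.6 to 18×0.9 + 12×0.2 = 18.6 | 0.07 to 0.52 |
| 15 of 30 | 15×0.8 + 15×0.1 = 13.5 to 15×0.9 + 15×0.2 = 16.5 | 0.004 to 0.15 |

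Follow-through matters as much as the share. If only 60% of the decided men would be screened within 12 weeks anyway, 24 of 30 decided gives just 0.08 to 0.13.

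H2 (at least 25), with p = 0.95 still intending and q = 0.30 to 0.50 of the others saying yes:

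| Decided at entry | Expected number intending | P(H2 met) |
|---|---|---|
| 24 of 30 | 24×0.95 + 6×0.3 = 24.6 to 24×0.95 + 6×0.5 = 25.8 | 0.535 to 0.795 |
| 15 of 30 | 15×0.95 + 15×0.3 = 18.75 to 15×0.95 + 15×0.5 = 21.75 | 0.002 to 0.094 |

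**Completer version in section 6.2.** Assume 20 completers, from the 65% retention benchmark (0.65 × 30 = 19.5). At least 60% then means 12 of 20. With the H1 inputs, the screening part alone is met with probability 0.84 to 0.99 if 16 of the 20 had decided, and 0.25 to 0.73 if 12 had. The joint rule, screening and intention together, was not computed.

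**When intention is asked.** H2 needs it at week 2. Section 6.2 places screening or intent at 12 weeks only. Table 2, as read, marks intention at baseline and 12 weeks but not at 2 weeks; its columns may have shifted in extraction. Until these are reconciled, it is unclear which pre-post comparison can be made.

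**The case against.** The best defence is that this is a 30-man pilot claiming preliminary effectiveness and a signal, with no error rate attached. The baseline data are also not thrown away: Table 2 collects intention, the section 5.4 question records decision stage, and section 6.2 says all variables will be described. Both points stand. They limit the consequence and narrow the gap to one thing: no stated use of baseline intention in the success rules or the change analyses.

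Four stronger readings are tempting and are not supported.

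- **That the study enrols men who already have a test booked.** No section mentions appointments or kits in hand. Having decided is an attitude, not a booking. Such men are not excluded, but nothing shows that they are expected.
- **That most entrants will already have decided.** No baseline share is given. Section 1.1 describes avoidance, fear and mistrust, section 4.1 reports lower screening participation, and the section 5.4 answers also include never having heard of CRC and having decided against screening.
- **That half the sample having decided is enough to pass H1.** That needs a high rate among the other men. At 40% for them, and 80-90% for the 15 decided men, the probability would be 0.42 to 0.68. The 40% has no source in the documents; at 10-20% the range is 0.004 to 0.15.
- **That efficacy should be judged only in undecided men.** The section 5.4 message to decided men points them to the in-app request for a clinic or navigator call. Turning a decision into a completed test is part of what the intervention does, so dropping these men would remove a group that it serves.

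**Conclusion.** The point holds. Entry is open to men who have decided, the success rules are follow-up percentages with no reference value, and intention is missing from the change analyses although a baseline measure exists. Following section 6.2 as written would count a man who intended throughout as evidence for the app.

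The size is conditional. On the assumed inputs, the thresholds are readily passed without any effect only when the share already decided is high: about 80% for H2, and about 60-80% with strong follow-through for H1. At 50% the risk is small for both (at most 0.15 for H1 and 0.09 for H2). The actual share is unknown, which is itself the reason to report it. This is a worthwhile correction to the analysis section of a pilot, not a flaw that invalidates the study.

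**What to change.** 1. **Reconcile the timing of intention** across H2 (week 2), section 6.2 (12 weeks only) and Table 2, so that baseline and the chosen follow-up use the same item.
2. **Section 6.2, intention.** Add intention to the pre-post change measures. Report the proportion intending at baseline and, among men not intending at baseline, the number and proportion who intend at follow-up. Show these beside the overall figure for the 80% threshold.
3. **Section 6.2, screening.** Report 12-week screening separately by baseline decision status, beside the overall figure for the 60% threshold. Word the efficacy statement in light of both, keeping all men in the efficacy population.
4. **Optional.** Add one baseline item on whether a test is already scheduled or a kit is in hand, for the same descriptive split. It must be in place before enrolment starts, because the answer is hard to recover reliably later.

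**Cost.** Items 2 and 3 are wording and use data that Table 2 already lists at baseline; item 4 is one question. Sample size and intervention do not change. The headline may look less favourable, and the subgroups will be small: with 24 of 30 decided, only 6 men remain in the other group, so these results would be descriptive. The changes still supply no rate without the intervention, so the conclusion remains that of a single-arm pilot.

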5.3 Outcome Variables

Please see the survey measures

Aim 3:

Primary Outcome: CRC screening status at 3 months

Secondary Outcomes:

- Enrolment
- Viewing videos (# views, # repeat views)
- Completion of baseline, 2 week and 12 week questionnaires (retention)
- Completing values elicitation activity

- Responding to request to contact clinic/navigation services
- Sharing any content with social network

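### Retention has two pass marks, above 75% in hypothesis H3 and 65% in the synopsis outcomes and section 6.2, so with 30 men a count of 20 to 22 both fails and passes

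*Combined protocol and SAP*

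**What the plan says.** The combined protocol and SAP states a retention criterion for the Aim 3 intervention in three places and lists retention without one in section 5.3.

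- **Synopsis, Objectives, H3.** The study will "maintain a retention rate (completion of baseline, 2 and 12 week surveys) >75" per cent.
- **Synopsis, Outcome Variables, secondary outcomes.** "Maintain a retention rate (completion of baseline, 2 and 12 week surveys) >65% at 12 weeks".
- **Section 6.2, feasibility paragraph.** "Feasibility will be assessed using a priori benchmarks for recruitment and retention". The retention benchmark counts as supported if at least 65% "complete both weeks 2 and 12 follow up".
- **Section 5.3, secondary outcomes.** "Completion of baseline, 2 week and 12 week questionnaires (retention"), with no threshold.

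On the number of men, section 6.1 says "we will test the intervention on 30 men". The retention rule in 6.2 does not say which men form the denominator, and it does not mention the baseline survey.

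**The concern.** The two synopsis entries define retention in the same words, completion of the baseline, 2-week and 12-week surveys, yet set different pass marks. A difference in definition therefore cannot explain the gap. The outcome list adds a 12-week time point, but H3 also runs to the 12-week survey, so timing does not separate them either. Section 6.2 repeats the lower figure with a different inequality sign. No text ranks the statements.

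An analyst reporting on H3 must use 75%, and an analyst applying 6.2 must use 65%. Both would be following the plan, and for some counts they would report opposite results from the same data. Section 6.2 presents its benchmarks as fixed in advance. With two pass marks in the text, the one to report can be chosen after the count is known.

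The unstated denominator is a lesser gap of the same kind. Section 5.4 says that one week after enrollment "men who have not engaged with the materials, completed the baseline questionnaire, or the navigation request will receive a text message". On its face this allows for enrolled men without a baseline questionnaire, so enrolled men and baseline completers may be different groups.

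**Working it through.** The plan derives no sample size, power or error rate from retention, so there is no figure of its own to reproduce. The check finds which counts give conflicting verdicts and how likely they are.

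**Inputs**
- Thresholds: above 75% (H3), above 65% (synopsis secondary outcomes), at least 65% (section 6.2).
- Denominator: n = 30, the intervention sample size in section 6.1. Using all 30 for the 6.2 rule is an assumption.
- True retention rate p: not given in the documents, so a range of 50% to 90% is assumed.

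**Step 1. Smallest passing count at n = 30**
- Above 75%: 0.75 × 30 = 22.5, so 23 men are needed (23/30 = 76.7%; 22/30 = 73.3% fails).
- Above 65% or at least 65%: 0.65 × 30 = 19.5, so 20 men are needed under either sign (20/30 = 66.7%; 19/30 = 63.3% fails).

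| Men retained | Rate | H3 (>75%) | Synopsis outcome (>65%) | Section 6.2 (≥65%) |
|---|---|---|---|---|
| 19 | 63.3% | fail | fail | fail |
| 20 | 66.7% | fail | pass | pass |
| 21 | 70.0% | fail | pass | pass |
| 22 | 73.3% | fail | pass | pass |
| 23 | 76.7% | pass | pass | pass |

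The conflicting counts are exactly 20, 21 and 22. The difference in sign at 65% has no effect here, because 19.5 is not a whole number.

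**Step 2. Chance of a conflicting count**

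Let X be the number retained, X ~ Binomial(30, p). The chance of a split verdict is P(20 ≤ X ≤ 22) = P(X ≥ 20) − P(X ≥ 23). For example, at p = 0.70 it is 0.730 − 0.281 = 0.449.

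| Assumed p | P(20 ≤ X ≤ 22) |
|---|---|
| 0.50 | 0.047 |
| 0.60 | 0.248 |
| 0.65 | 0.384 |
| 0.70 | 0.449 |
| 0.75 | 0.380 |
| 0.80 | 0.214 |
| 0.85 | 0.067 |
| 0.90 | 0.008 |

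**Step 3. Other denominators**
- n = 28: 0.75 × 28 = 21 exactly, so above 75% needs 22. 0.65 × 28 = 18.2, so 19 are needed. Conflict at 19 to 21.
- n = 25: 0.75 × 25 = 18.75, so 19 are needed. 0.65 × 25 = 16.25, so 17 are needed. Conflict at 17 and 18.

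These two denominators are illustrations and do not come from the plan. They show that the conflict remains while its location moves.

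**The case against.** The best counter-argument is that the operative rule can be inferred. The 65% figure appears in two of the three places, including the only analysis section, which words it as a decision rule set in advance. A hypothesis at 75% could sit beside a support benchmark at 65% without logical contradiction. This does not settle the matter: H3 is also prespecified with its own pass mark, the synopsis itself attaches both figures to one definition, and no text gives 6.2 precedence.

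The denominator point is open to more dispute. H3 speaks of a sample of 30, and the neighbouring benchmarks in 6.2 refer to consented men, so the intended denominator can be guessed. The reminder sentence in section 5.4 also says the message draws on what men reported at baseline, which fits poorly with men who have no baseline data. Section 5.4 further opens the rest of the app only after the baseline questionnaire, so a man who completes both follow-ups would normally have completed baseline. Leaving baseline out of 6.2 therefore probably matters little for the numerator. What stands is that the 6.2 retention rule names no denominator.

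Finally, the stakes are limited. No go/no-go decision, stopping rule or error rate depends on this benchmark, and the observed retention proportion can be reported whichever threshold applies. The split-verdict probabilities rest on assumed retention rates, so they show how far the conflict could matter, not how likely it is in this study. These limits are accepted.

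**Conclusion.** The concern holds. The current text gives one retention measure two pass marks and does not say which decides. With 30 men as the denominator, 20, 21 or 22 retained means H3 is not met while the 6.2 benchmark is supported; 19 or fewer, or 23 or more, gives the same answer under all three statements.

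The chance of a split verdict is about 21% to 45% if true retention lies between 60% and 80%, and 7% or less at 50%, 85% or 90%. These figures assume a common retention probability, independence between men and all 30 men counted.

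The consequence is confined to the secondary feasibility conclusion. Feasibility is nevertheless a stated purpose of Aim 3, and retention is one of the two measures 6.2 names for judging it, so the plan should be corrected. The unstated denominator is a secondary part of the same correction.

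**What to change.** Before outcome data are seen, state one retention threshold, with one inequality sign and one denominator (for example, all consented men), in H3, the synopsis secondary outcomes and section 6.2, and refer to it from section 5.3. Use the same survey list in each place, so that 6.2 says whether baseline completion is required.

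The shortest edit is to bring H3 into line with the 65% rule. The documents justify neither value, so the investigators should choose one and give the reason. Alternatively, keep both figures and label 75% as the target and 65% as the minimum that decides feasibility.

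The cost is a few words, with no change to sample size or procedures. The choice does affect how hard the benchmark is to meet: at an assumed true retention of 70%, the chance of passing is 73% under the 65% rule and 28% under the 75% rule.
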